12.4 Trial Treatment

12.4.1 Trial Vaccine Exposure

A summary of doses administered, including reasons for doses not administered is provided for the SAS.

12.4.2 Prior and Concomitant Medications and Vaccinations

Prior and concomitant medications and vaccinations are coded using World Health Organization Drug Dictionary (WHODRUG), Version September 2020 Global B3 or higher. Concomitant medications are summarized based on the SAS. .

Concomitant medications/vaccinations (see Section 10.4) are summarized by Anatomical Therapeutic Chemical (ATC) level 1 WHODRUG PN as the number and percentage of subjects taking at least one medication within each medication group and subgroup.

Prior medications/vaccinations (see Section 10.4) are provided in a data listing along with the concomitant medications/vaccinations.

12.5 Important Protocol Deviations

Per PRA/ICON processes, protocol deviations data is entered into PRA/ICON system of record (PSO). The trial team and the Sponsor conduct on-going reviews of the deviation data from PSO and the resulting set of evaluable subjects throughout the trial, adjusting the deviation criteria as seems appropriate.

Protocol deviation data is reviewed prior to each formal analysis (i.e. interim analyses or final analyses) and important deviations leading to elimination of subjects from analysis sets are identified. Detailed definitions and further guidance on programmatic approaches for identification of protocol deviations and/or other criteria leading to exclusion from the analysis sets are provided in a separate Appendix to the SAP (see 5). The detailed definitions of important protocol deviations leading to exclusion of subjects from analysis sets are provided in the final version of the SAP and/or in the final signed minutes of the data review meetings prior to each formal analysis and prior to database lock.

A summary of important subject-level protocol deviation data is created based on the SAS, displaying the number and percentage of subjects with any important protocol deviations and broken down by type of deviations.

Site- and subject-level protocol deviation data is listed.

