### **10.2.3 Per Protocol Immunogenicity Subset**

The PPI will include 250 subjects who belong to the Immunogenicity/Reactogenicity Subset (200 verum subjects, i.e. 100 per lot and 50 placebo subjects) and who:

- Received both doses as randomized and within the windows defined in the protocol.
- Have no major protocol deviations expecting to impact the immunogenicity outcomes as specified in the SAP.
- Have not received medical treatments (such as blood products, immunoglobulin therapy) that may interfere with 1 or both of the proposed immunogenicity measurements.
- Have a blood sample collected at 14 days (Day 43) post-second vaccination available for analysis.

The PPI will be the primary analysis population for SARS-CoV-2 RBD of S protein antibody responses and SARS-CoV-2 viral neutralizing antibody.

For assessment of seroconversion rates, the analyses will be restricted to PPI subjects who are naïve at baseline to SARS-CoV-2 RBD of S protein antibody or to SARS-CoV-2 viral neutralizing antibody depending on the endpoint analyzed.

The lot-to-lot consistency analysis on SARS-CoV-2 RBD of S protein antibody titers will be done on the PPI subjects who received 2 doses of CVnCoV vaccine coming from the same lot and who have a negative SARS-CoV-2 RBD of S protein antibody titer at baseline.

Subjects to be excluded from the PPI will be identified and reviewed at the Blinded Data Review Meeting held before unblinding of the trial. Major protocol deviations will be listed and summarized.

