	
 • Section 9.5.2 Added that Subjects who received an alternate / licensed / authorized vaccine prior to 15 days after the second vaccination will be excluded from IS. • Section 9.5.5: 
 ○ Reworded the EAS definition to make it clearer. ○ Added unblinding and alternate / licensed / authorized vaccine receipt. ○ Added use of adjudication data. • Section 9.5.6: Modified EASS definition to not exclude subjects after unblinding. • Section 10.6.1: Added serology status at baseline and serology status at Visit Day 43 definition. • Section 10.7.4: Corrected formula for Symptom onset \geq 15 days after second trial vaccination. • Section 10.11: Added date of alternate / licensed / authorized vaccine + 1 to the censoring date formula. • Section 10.12: Added section regarding age groups. • Section 11: 
 ○ Removed planned interim analysis. ○ Added possible ad-hoc analyses around early conditional approval in Europe. • Section 12.1: 
 ○ Screen failures were removed. ○ Description of tables was adapted to match the required outputs. ○ Summary of censored subjects was added. ○ Summary of stratification and treatment errors was added. • Section 12.2: Added combined (adjudication + EDC) serology status variable • Section 12.3: 
 ○ Adapted analysis description of medical/surgical history to match required analyses. ○ Added co-morbidities analysis. • Section 12.5: Added subject- and site-level for protocol deviations. • Section 12.6.1.1 Re-arranged solicited and unsolicited AE analysis descriptions to reflect the required analyses, added Section 12.6.1.3. • Section 12.7: Added that no "Total" summaries will be provided for immunogenicity. • Section 12.8.1.1: Added usage of adjudication data for serostatus at baseline and Visit Day 43. • Section 12.8.1.4: Added sensitivity analysis for one secondary endpoint. • Appendix 2: 
 ○ Removed Multisystem inflammatory syndrome in children from AESI list ○ Removed COVID-19 disease from AESI list

4.0 / 08 Apr 2022
	
 • Section 1.0: Updated signatories details • Section 6.0: Added info that main stakeholders are unblinded at time of SAP update • Section 6.1: Changes from protocol were updated

- Section 7.2.1: Secondary efficacy objective on asymptomatic cases was deleted.

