6.0 Introduction

The SAP describes the statistical methods to be used during the reporting and analyses of data collected under CureVac AG Protocol CV-NCOV-005.

The SAP should be read in conjunction with the trial protocol version 5.0 dated 22-Dec-2021 and Case Report Form (CRF) v4.0 dated 10-Jun-2021.

This SAP describes the statistical methods used for the final analysis. The SAP v1.0 is approved prior to the first relevant delivery¹. Changes following approval of the first version of the SAP are tracked in the SAP Change Log and the last final SAP version is approved prior to final database lock.

Each version of the SAP requires approval by the Sponsor.

It must be noted that all main stakeholders from the combined Sponsor and designated Contract Research Organization (CRO) (PRA/ICON) study team have been unblinded between approval of SAP versions 3.0 and 4.0. As a consequence, the SAP version 4.0 is created and approved by an unblinded authorship/approval team.

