The randomization scheme is generated and maintained by an independent statistical group at PRA/ICON. Subjects are enrolled into the trial online and randomized using an Interactive Web Response System (IWRS). The first 1,260 subjects enrolled are planned to be included in the Immunogenicity/Reactogenicity Subset.

See Section 10.10 for handling of cases where a subject becomes eligible to receive an AV during the course of the trial.

In Study Protocol 3.0 the following decision regarding unblinding was added: "*Since the efficacy results from the HERALD study for CVnCoV are available and all subjects in the CV-NCOV-005 study are currently eligible to receive an authorized vaccine, all subjects in this CV-NCOV-005 study will be unblinded.*" This unblinding is performed on a by-subject level via IWRS and therefore does not require any additional programmatic or planning attention.

In July 2021, on the occasion of Herald CV-NCOV-004 study primary efficacy analysis delivery, selected members from the Sponsor and PRA/ICON study teams (i.e. both Biostatistics teams) were unblinded for CV-NCOV-005. In December 2021 the full Sponsor and PRA/ICON study teams were unblinded.

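### SAP 12.5 leaves the deviation criteria that decide membership of the primary immunogenicity set open to adjustment by study teams who were fully unblinded by December 2021

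*SAP*

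**What the plan says.** SAP 12.5 describes an on-going review by the trial team and the Sponsor, for as long as the trial runs, of the deviation data and of which subjects remain evaluable as a result, "adjusting the deviation criteria as seems appropriate". Before each formal analysis, "important deviations leading to elimination of subjects from analysis sets are identified". The final definitions may stand in the last SAP version, in signed data review minutes, or in both, provided this is done before the analysis and before database lock. The detailed rules are in Appendix 5, which is kept outside the SAP.

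On blinding, SAP 8.6 reports that in July 2021 "selected members from the Sponsor and PRA/ICON study teams (i.e. both Biostatistics teams) were unblinded for CV-NCOV-005", and that "In December 2021 the full Sponsor and PRA/ICON study teams were unblinded". SAP 6.0 adds that "the SAP version 4.0 is created and approved by an unblinded authorship/approval team". The change history dates that version "4.0 / 08 Apr 2022".

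On the PPI, the protocol states: "Subjects to be excluded from the PPI will be identified and reviewed at the Blinded Data Review Meeting held before unblinding of the trial". SAP 9.5.4 keeps the name Blinded Data Review Meeting but ties it to the time before any formal analysis. Among its conditions for the PPI is the absence of major deviations that could affect immunogenicity, with Section 12.5 named as the place where these are specified.

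**The concern.** A per-protocol set can be defended when its exclusion rules were settled by people who could not see what the rules would do to the result. Here the permission to adjust has no end date, no blinding condition and no requirement to log changes, and it survives in a SAP version written after the people who hold it had been unblinded. What they review includes the set of evaluable subjects that the criteria produce.

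At stake are the geometric mean titres and seroconversion proportions in the PPI, including the primary immunogenicity endpoint. If criteria can move after treatment is known, and possibly after titres are known, the plan cannot show that exclusions were independent of arm and response, even if everyone acted properly.

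This point is about deviation-based exclusions. How the Sponsor picks the 250 subjects from those who remain is a separate matter.

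**Working it through.** The plan states no figure on this point, so the check is mainly a comparison of texts and dates.

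**1. Does the clause reach the PPI?** Yes. SAP 9.5.4 refers to Section 12.5 by number, and SAP Table 3 assigns the primary and secondary immunogenicity endpoints to the PPI.

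**2. Does it reach the Efficacy Analysis Set (EAS)?** Only through general wording. SAP 12.5 and Appendix 5 speak of analysis sets without exempting any. However, SAP 9.5.5 and Protocol 10.2.4 define the EAS by listed conditions (doses as randomised, no early case, not stopped early, seronegative to N protein and, in the SAP, no early unblinding or authorised vaccine). Neither contains a major-deviation condition or points to 12.5.

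**3. Was the safeguard moved?** The protocol sets the PPI review before the trial is unblinded; the SAP sets it before the formal analysis. For the end-of-trial analysis the second condition can be met after December 2021, when the first no longer can. SAP 6.1 has a general entry on updating the analysis sets for unblinding and authorised vaccine use, but nothing on the timing of this review.

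**4. How long is the window?** SAP 8.6 gives months only, so a range is needed.
- Full teams, 1 to 31 December 2021 until 8 April 2022: 128 to 98 days.
- Biostatistics teams, 1 to 31 July 2021 until 8 April 2022: 281 to 251 days.

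SAP 6.0 places the last SAP approval before final database lock, so these are minimum lengths.

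**5. Which version is the last blinded one?** SAP 3.0 is dated 15 July 2021, and SAP 6.0 says the main stakeholders were unblinded between versions 3.0 and 4.0. The July biostatistics unblinding has no day: if it fell on 1 July, version 3.0 came 14 days after it; if on 31 July, 16 days before it. SAP 6.0 supports the second order, but the exact date needs confirming.

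**6. When could titres by arm be known?** SAP 8.2 and 8.6 place the first immunogenicity delivery in August 2021, with the CRO that produced it unblinded on that occasion.

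**7. What could one exclusion do?** No titres or spread are given, so only the sensitivity can be shown. The geometric mean of n titres is exp(Σ ln x / n). If the set is held at n = 100 per lot, an excluded subject is replaced by another. If the replacement's titre is f times higher, the geometric mean is multiplied by f^(1/n). Taking the 2-fold and 4-fold steps that SAP 12.7.1 reports as illustrative values of f:
- f = 2: 2^(1/100) = exp(0.6931/100) = 1.007, a rise of 0.7%.
- f = 4: 4^(1/100) = exp(1.3863/100) = 1.014, a rise of 1.4%.

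Swaps in the same direction multiply. How many subjects any criterion would affect is not known.

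**The case against.** The strongest reply has four parts.

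- *Recording in minutes is allowed.* Protocol 11.3 itself lets elimination definitions stand in the final SAP or signed review minutes, and Protocol 10.3.1 lets the SAP be finalised up to database lock. This stands: the minutes route is not a departure. But lock fixes when the rules stop moving, not who may move them, and Protocol 10.2.3 adds the blinding condition for the PPI.
- *No change is shown.* This also stands. The version 4.0 change log does not list Section 12.5, so the clause appears to be carried over, and Appendix 5 may already be frozen. The documents do not settle it.
- *The meeting is still called blinded.* It could be so if attended only by people without access to assignments. The SAP does not say that, and 12.5 gives the review to the trial team and the Sponsor.
- *Consequences are limited.* Immunogenicity and efficacy are descriptive, with no hypothesis or success criterion, and the Safety Analysis Set needs only randomisation and one dose. So there is no type I error issue and the main safety results are untouched. Selection bias in the reported estimates remains possible.

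Some stronger readings are tempting but not supported. A reader might infer that vaccine efficacy is equally exposed. With hypothetical counts of 20 cases per group and a person-time ratio of 2, VE = 1 − (20/20)/2 = 50%; losing two vaccine cases gives 1 − (18/20)/2 = 55%, and losing two placebo cases gives 1 − (20/18)/2 = 44.4%. The arithmetic is right, but the counts come from neither document, and the EAS conditions contain no deviation rule by which a case would be removed. Nor do the documents show that the teams held titres from July 2021, or that the protocol required exclusions from every set to be settled before unblinding; that sentence covers the PPI only.

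**Conclusion.** The concern holds for the PPI. A stated rule gives unblinded staff discretion over membership of the set for the primary immunogenicity endpoint, and the protocol's condition that exclusions be reviewed before unblinding has been loosened without being declared in SAP 6.1. For the EAS the exposure is possible only through general wording.

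The discretion stayed open for at least 98 days after full unblinding. Its effect on the titres cannot be estimated from the documents: about 0.7% to 1.4% of a lot's geometric mean per substituted subject, assuming 100 per lot and a twofold to fourfold difference in titre, so several exclusions in one direction would be needed for a visible shift. The conclusion does not depend on anyone having used the discretion, and no misuse is implied. It would fall away for the PPI if Appendix 5 proved to have been frozen before the unblinding and applied unchanged.

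**What to change.** - Delete the adjustment clause in SAP 12.5 for the period after unblinding.
- Freeze the deviation-based exclusion criteria in Appendix 5 at the last version approved while the team was blinded. On the SAP's account this is the version in force at SAP 3.0 (15 July 2021); the sponsor should confirm that date against the July biostatistics unblinding.
- Apply those criteria by program to the PPI, and to any deviation-based exclusion from other sets.
- Use criteria added later only in a labelled sensitivity analysis, each with a date and a reason.
- Take any manual exclusion decision on listings without arm, titre or case status.
- List the changed timing of the PPI review in SAP 6.1.

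The EAS conditions in SAP 9.5.5 stay as they are, including the one on unblinding and authorised vaccine that entered with version 3.0. A freeze set simply before July 2021 would fall back to version 2.0 and lose that condition, so it should not be used.

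The cost is SAP wording, a set of masked listings and possibly one extra table. No new data are needed.

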12.6 Safety Analyses

12.6.1 Adverse Events

Unsolicited AEs, including SAEs, and AESIs and solicited AEs integrated to or recorded on the CRF are coded using MedDRA Version 23.1 or higher by SOC and PT.

Only TEAEs as defined in Section 10.5.1 are included in AE summaries. In AE listings, all AEs are included.

Solicited AEs occurring on the day of vaccination and the following 7 days are generally included in summaries if not otherwise stated.

Summaries of medically attended AEs only include those AEs that started up to 6 months after the second trial vaccination, see Section 10.5.6 for further details.

Note that for all summaries by SOC and PT, counting is by subject, not event and subjects are only counted once within each SOC and PT. However, if not stated otherwise, all summaries of unsolicited AEs include the number of AEs reported in each category and all events of a subject are then counted.

All AE summary tables are provided overall, by vaccine group (placebo, pooled CVnCoV lot, and split by lot), and are repeated separately in subjects seronegative at baseline and in subjects seropositive at baseline for SARS-CoV-2 N protein antibody levels (see Section 10.6.1).

In general, percentages are based on the number of subjects in the respective analysis set. In summary tables for AEs after the second vaccination, percentages are based on the number of subjects in the respective analysis set who have received the second vaccination.

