- Must be a virologically-confirmed case of COVID-19 defined as a positive SARS-CoV-2 specific RT-PCR test in a person with clinically symptomatic COVID-19 (see Section 9.2).
- Symptom onset must have occurred  $\geq$  15 days following the second trial vaccination.
- The subject must not have a history of virologically-confirmed COVID-19 at enrollment (based on exclusion criterion 1) or have developed a case of virologically-confirmed COVID-19 before 15 days following the second trial vaccination (see Section 10.2.4, EAS population for more details).
- The subject must have been demonstrated to be SARS-CoV-2 naïve at baseline and at Day 43 (seronegative to N protein).

These efficacy cases might be confirmed by the Adjudication Committee.

The DSMB will periodically monitor COVID-19 cases across CV-NCOV-004 and CV-NCOV-005 for signals of VDE with pre-specified criteria for halting based on these signals.

An interim analysis is planned. The cut-off date for the interim analysis in CV-NCOV-005 will be based on the regulatory requirements to obtain early conditional approval in Europe. All subjects will be unblinded after the final analysis results of trial CV-NCOV-004. Subjects of the study CV-NCOV-005 who were assigned to CVnCoV will continue, until the end of the trial {when the last subject has completed the last visit on Day 393 (see Section 5.4)}. During this period, accrual of COVID-19 cases will continue. Subjects who were assigned to placebo will not continue after unblinding and will be invited to an End of Trial visit for a final safety examination.

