### **5.4 End of Trial Definition**

A subject is considered to have completed the trial when he/she has completed all visits, and procedures and tests applicable for the group to which he/she was randomized to.

End of trial CV-NCOV-005 is defined as when the last subject who received CVnCoV has completed the last visit on Day 393 or prematurely discontinued the trial. Placebo subjects will discontinue the trial once study protocol version 3.0 and 4.0 are approved.

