## 8.2 Withdrawal from the Trial

Subjects should be withdrawn from the trial in case any of the following situations occur:

- Continued participation jeopardizes the subject’s health, safety, or rights.
- The subject has experienced an AE that requires early termination because continued participation imposes an unacceptable risk to the subject’s health or the subject is unwilling to continue because of the AE. The reasons for not performing further safety or immunogenicity assessments should be documented.
- The subject did not return to the site and multiple attempts (a minimum of 3 attempts) to contact the subject were unsuccessful (lost to follow-up).
- The subject wishes to withdraw from the trial. The reason for withdrawal, if provided, should be recorded; this could include the availability of an approved COVID-19 vaccine.

All attempts should be made to determine the underlying reason for the withdrawal and, where possible, the primary underlying reason should be recorded (i.e., withdrawal due to an AE should not be recorded in the “voluntary withdrawal” category).

Any subject who prematurely terminates participation and who has received at least 1 trial vaccine dose will undergo the same procedures as for the end of trial visit, unless such procedures are considered to pose unacceptable risk to the subject.

After trial unblinding, i.e. after approval of study protocol version 3.0 and 4.0, all placebo subjects should be withdrawn at the earliest possible timepoint, if their originally planned End of Trial visit is later than February 2022 and will undergo the same procedures as for the End of Trial visit at their withdrawal visit. If a withdrawal visit cannot be scheduled for placebo subjects due to the pandemic setting, the end of trial assessment, i.e. collection of final safety data, can also be done by phone. In the e-CRF, the withdrawal reason for placebo subjects should be documented as “placebo subject withdrawn after trial unblinding”.

Discontinued or withdrawn subjects will not be replaced.

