For subjects who received CVnCoV, the end of trial visit will be performed on Day 393, 1 year after the last trial vaccine administration. For subjects who received placebo, the end of trial visit will be conducted after unblinding. If possible, this visit should also include subjects who prematurely discontinued vaccination during the trial. The following assessments should be performed:

- Review and record any newly reported AEs since the phone contact on Day 302 (SAEs).
- Record concomitant medications and vaccinations, according to instructions in Section 7.6.
- Record symptoms suggestive of COVID-19 or any confirmed COVID-19 case.
- Perform a complete physical examination, including height and weight (see Section 9.3.6).
- Measure vital signs (body temperature, pulse, blood pressure, see Section 9.3.6).

**9.1.2 All Other Subjects and subjects that, following unblinding, receive an authorized vaccine after having received at least one dose of CVnCoV**

Following enrollment of subjects into the Immunogenicity/Reactogenicity Subset (n=1,260), the remaining 1,260 subjects, 18 years of age and older, will be enrolled to this group.

Also, all subjects initially enrolled to the Immunogenicity/Reactogenicity Subset that receive an authorized vaccine following at least one dose of CVnCoV will be included in this group from the day when the authorized vaccine is administered (Schedule of Activities- Table 2).

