6.1 Changes from Protocol

- 1) Addition of sensitivity analysis on Safety outputs for Safety Interim Analysis (IA) to account for censoring rules in main analyses (Section 12.6.6)
- 2) Inclusion of Adverse Events (AEs) Related to Standardized and Customized Medical Dictionary for Regulatory Activities (MedDRA) Queries (CMQs)
- 3) The planned IA to obtain early conditional approval in Europe was removed.
- 4) An early immunogenicity delivery and related unblinding of PRA/ICON was added.
- 5) Update to analysis sets (Section 9.5) to account for unblinding and/or Authorized Vaccine (AV) application.
- 6) Protocol deviations are classified in site- and subject-level protocol deviations.
- 7) A sensitivity analysis on a secondary endpoint was added, according to what was done in the CV-NCOV-004 study.

¹ This was the safety delivery for the rolling submission when subjects randomized by (including) 11-Feb-2021 had reached 6 weeks post 2nd dose.

- 8) Multisystem inflammatory syndrome in children was removed from Adverse Event of Special Interest (AESI) list
- 9) The Efficacy Analysis Set (EAS) excludes subjects who were unblinded prior to 15 days after the second vaccination or received an AV prior to 15 days after the second vaccination
- 10) In the protocol synopsis the definition of the efficacy endpoint does no longer require the subject to be N negative. This is considered an erroneous deletion and is ignored.
- 11) "Non-serious intercurrent medical conditions that may affect the immune response to vaccination will also be collected throughout the trial." is taken out of the AESI definition.
- 12) The secondary immunogenicity endpoint lot to lot consistency is not to be analyzed.
- 13) From the secondary efficacy endpoint "Occurrence of first episodes of virologically-confirmed (RT-PCR positive) symptomatic cases of COVID-19 meeting the case definition for the efficacy analysis by severity (mild, moderate, severe and moderate to severe COVID-19)" only the mild cases are analyzed .
- 14) No repeat of any of the secondary efficacy analyses on the Safety Analysis Set (SAS) is done.
- 15) Protocol Section 10.3.7.1 requires the secondary efficacy analyses of prevention or reduction of asymptomatic infections as measured by seroconversion to the N protein to be performed, although this was deleted from all other sections in the protocol. This is considered an oversight and therefore this analysis is not performed.

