8.3 End of Trial

A subject is considered to have completed the trial when he/she has completed all visits, procedures, and tests applicable for the group to which he/she was randomized to at trial entry. Exception: Placebo subjects discontinue the trial once study protocol version 3.0 and 4.0 are approved. The corresponding wording from the protocol is as follows: *“After trial unblinding, i.e. after approval of study protocol version 3.0 and 4.0, all placebo subjects should be withdrawn at the earliest possible timepoint, if their originally planned End of Trial visit is later than February 2022 and will undergo the same procedures as for the End of Trial visit at their withdrawal visit. If a withdrawal visit cannot be scheduled for placebo subjects due to the pandemic setting, the end of trial assessment, i.e. collection of final safety data, can also be done by phone. In the e-*

CRF, the withdrawal reason for placebo subjects should be documented as “placebo subject withdrawn after trial unblinding”.

End of Trial (EOT) is defined as the point at which the last subject has completed the last visit on Day 393 or (prematurely) discontinued the trial.

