12.6.1.4 Repeats of AE Analyses without Censoring

In the EOT analysis the following outputs are repeated without applying any censoring rules due to subject unblinding or AV receipt:

- Overall summary of unsolicited AEs occurring through 28 days after any dose
- Unsolicited AEs, SAEs, unsolicited AESIs and AEs with fatal outcome, by SOC and PT occurring through EOT Visit

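### The uncensored through-EOT tables of SAEs, AESIs and fatal AEs (SAP 12.6.1.4) set crude percentages side by side for arms with unequal planned follow-up, and SAP 12.6.7 gives no fitting denominator for its four exposure groups

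*SAP*

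**What the plan says.** SAP 12.6.1 presents AE summaries by vaccine group (placebo, pooled CVnCoV, each lot) and overall, and sets the default denominator: "In general, percentages are based on the number of subjects in the respective analysis set". For tables after the second dose, only subjects who received that dose are counted. Neither rule involves time at risk.

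SAP 12.6.1.4 adds a second set of tables: "In the EOT analysis the following outputs are repeated without applying any censoring rules due to subject unblinding or AV receipt". The set covers unsolicited AEs, SAEs, unsolicited AESIs and fatal AEs through the EOT visit.

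The EOT visit falls at different times in the two arms. Protocol 9.1.1.10: "For subjects who received CVnCoV, the end of trial visit will be performed on Day 393, 1 year after the last trial vaccine administration". For placebo there are two accounts:

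- All leave. Protocol 5.1: "Subjects who were assigned to placebo will not continue after unblinding". Protocol 5.4: "Placebo subjects will discontinue the trial once study protocol version 3.0 and 4.0 are approved". SAP 8.3 opens in the same way: "Exception: Placebo subjects discontinue the trial once study protocol version 3.0 and 4.0 are approved".
- Some leave. Protocol 8.2: "all placebo subjects should be withdrawn at the earliest possible timepoint, if their originally planned End of Trial visit is later than February 2022". SAP 8.3 then reproduces this conditional rule.

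SAP 12.6.7 adds uncensored outputs in which each event goes to one of four exposure groups (placebo only, CVnCoV only, CVnCoV then AV, AV without CVnCoV) according to what had been given before onset. The only population named is the Safety Analysis Set (SAS).

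Follow-up time is defined in SAP 10.11, Table 8, for the COVID-19 and burden-of-disease endpoints only.

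**The concern.** Safety is a primary objective, and Protocol 10.3.5 plans no formal testing of it, so readers will judge from the descriptive percentages. The 12.6.1.4 repeats are the by-arm tables that cover the whole window of the primary safety endpoints for SAEs, AESIs and deaths. If one arm is observed longer by design and the denominator stays the number of subjects, background events accumulate for longer in that arm. An apparent CVnCoV excess can then arise with no true difference.

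In 12.6.7 one subject can pass through two states, for example CVnCoV only and then CVnCoV followed by AV. A percentage of the whole SAS does not show how many subjects reached a state or how long they spent in it.

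**Working it through.** **The plan's own safety figure.** SAP Table 1 gives 81.4% for seeing at least one event of incidence 1:1000 among 1,680 subjects: 1 − (1 − 0.001)^1680 = 0.814. It reproduces and is not disputed, but it is a per-subject calculation without follow-up time.

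**Inputs from the documents.** Planned arms are 1,680 CVnCoV and 840 placebo. CVnCoV follow-up is 393 days. Protocol version 4.0 is dated 11 August 2021 and version 5.0 is dated 22 December 2021. The SAP footnote printed under Section 6.1 dates the first safety delivery to the time "when subjects randomized by (including) 11-Feb-2021 had reached 6 weeks post 2nd dose"; SAP 12.6.6 describes a delivery at the same milestone for the first 1,037 subjects. I read these as one delivery.

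**Assumptions.** The hazard is constant and equal in both arms. Day 1 is 11 February 2021. All CVnCoV subjects are followed to Day 393. Version dates stand in for placebo exit, because approval and exit dates are not given.

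**Trial days.** With Day 1 on 11 February 2021, 11 August 2021 is Day 182, 22 December 2021 is Day 315 and Day 393 is 10 March 2022.

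**Share outside the Protocol 8.2 exception.** A planned Day 393 no later than 28 February 2022 needs Day 1 by 1 February 2021. Everyone after the first 1,037 is later than that, so at planned enrolment at least (2,520 − 1,037)/2,520 = 1,483/2,520 = 58.8% fall outside. If only 2,000 were enrolled, the figure is 963/2,000 = 48%.

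**Crude ratio, CVnCoV to placebo.** For rare events it is close to the ratio of mean follow-up, 393 / (q × D + (1 − q) × 393), where a share q of placebo leaves on Day D.

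- All leave: 393/182 = 2.16; 393/315 = 1.25.
- 58.8% leave: 393/(0.588 × 182 + 0.412 × 393) = 1.46; with D = 315, 1.13.
- 48% leave: 393/(0.4815 × 182 + 0.5185 × 393) = 1.35; with D = 315, 1.11.
- Placebo completes: 1.0.

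**Example.** Assume a 2% risk to Day 393 in both arms, with all placebo leaving at Day 182. CVnCoV shows 33.6/1,680 = 2.00% and placebo 7.8/840 = 0.93%. An exponential model gives a ratio of 2.15. Person-years are 1,680 × 393/365.25 = 1,808 and 840 × 182/365.25 = 419, so both rates are 1.86 per 100 person-years.

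**SAP 12.6.7.** Assume the same 2% risk and that half of the CVnCoV subjects take AV at Day 120. The CVnCoV-then-AV group has about 11.6 events. That is 0.69% of all 1,680 CVnCoV subjects, or about 1.39% of the 840 who took AV. The CVnCoV-only group has 22.0 events, 1.31% of 1,680. Person-years are 840 × 273/365.25 = 628 and 840 × (393 + 120)/365.25 = 1,180, giving about 1.85 and 1.86 per 100 person-years. The hazard is the same in both groups, and the impression depends on the denominator chosen.

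**The case against.** The main safety tables are censored in both arms by one rule (SAP 10.10) and are kept unchanged (SAP 12.6.7, item 1). The 12.6.1.4 tables are a supplement and report the endpoint as SAP 9.1.1 defines it, through the EOT visit. SAP 12.1 tabulates early withdrawals with reasons, and Protocol 8.2 prescribes a specific reason for placebo subjects withdrawn after unblinding, so the differential exit will be visible. The sizes are also soft. CVnCoV recipients are only encouraged to stay (Protocol 8), and Protocol 8.2 names availability of an approved vaccine as a possible reason for withdrawal. The amendment history records the placebo withdrawal procedure as added only in version 5.0, which suggests later exit for at least some. Finally, the list of tables (SAP Appendix 4) is held outside the SAP and could not be checked.

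Much of this stands. The censored tables are the like-for-like contrast, and attrition under CVnCoV would shrink every ratio above. Subjects randomised before 11 February 2021 would be on a later trial day at a given exit date, and those randomised afterwards on an earlier one. But a disposition table shows that placebo subjects left; it does not correct the percentages. Nothing in the reviewed text gives time at risk for these tables. Naming the SAS in 12.6.7 states a population, but not one that fits each exposure state.

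**Conclusion.** The point holds for the uncensored SAE, unsolicited-AESI and fatal-AE tables through EOT. If hazards are equal and follow-up is as planned, the distortion runs towards a CVnCoV excess. Its size is not determinable from the documents: 1.0 to about 2.16 on the dates and shares used, resting on a constant hazard, a single Day 1, full CVnCoV follow-up and version dates in place of exit dates. Crude percentages are not distorted for events clustered soon after dosing.

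Four stronger inferences are not supported:

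- That the main safety tables share the fault. They censor both arms by the same rule; they simply cover a shorter window than the endpoint.
- That the version 3.0 date (23 July 2021, Day 163) may be used, giving 393/163 = 2.41. Protocol 5.4 and 8.2 and SAP 8.3 tie exit to approval of versions 3.0 and 4.0.
- That all placebo subjects certainly left early. Protocol 8.2 and the text copied into SAP 8.3 say otherwise, and the conflict is unresolved.
- That the through-EOT unsolicited-AE table needs the same rate. General unsolicited AEs are collected only for 28 days after each dose and only in the subset (SAP 10.5 and 10.5.4), and later ones outside the special categories are kept out of tables (SAP 10.5.8).

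**What to change.** Keep the crude counts and percentages, and the 7-day and 28-day tables as they are. Then:

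- For the SAE, AESI and fatal-AE tables in 12.6.1.4, add follow-up time by arm and subjects with a first event per 100 person-years, with exact Poisson 95% CIs. Count time from first dose to the earlier of first event or end of follow-up, and add these endpoints to Table 8.
- Do not add a person-year rate to the through-EOT unsolicited-AE table. It would count time in which those events cannot be tabulated.
- In 12.6.7, give for each exposure state the number of subjects entering it and the person-time in it, split at AV receipt.
- Name the censored main tables as the like-for-like between-arm comparison and show their follow-up time.
- Reconcile Protocol 5.1 and 5.4 with Protocol 8.2, and the two statements within SAP 8.3, on which placebo subjects leave early.

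The cost is SAP wording and some programming from dates already collected. The drawback is that person-year rates assume a roughly constant hazard. If events cluster after dosing, the longer-followed arm is diluted: with 393 v 182 days, equal dose-related risk gives a rate ratio of 182/393 = 0.46, and a true two-fold excess gives 2 × 0.46, about 0.93. The CVnCoV rate in 12.6.1.4 also mixes time before and after AV. The rates must therefore be read beside the crude percentages, the 28-day tables and the censored tables, not in place of them.
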